2. INTRODUCTION

Etrasimod is an orally administered, selective, synthetic $S1P_{1,4,5}$ modulator that is being developed to treat immune-mediated inflammatory disorders, including UC, AA, AD, CD and EoE. The $S1P_1$ is a cell surface expressed protein that has been shown to regulate lymphocyte migration out of lymphoid tissues. Synthetic small molecule $S1P_1$ agonists have been observed to act as functional antagonists by inducing sustained receptor internalization, thus inhibiting lymphocyte migration out of lymphoid tissues and lowering the amount of peripheral blood lymphocytes available to be recruited to sites of inflammation. Modulation of the S1P/S1P receptor axis is thought to be a potential therapeutic approach to the management of immune-mediated inflammatory disorders.

The purpose of the study is to estimate the rBA of etrasimod mini tablets 2 mg in water and 3 food vehicles relative to etrasimod clinical IR tablet 2 mg under fasting conditions in healthy adult participants. The study will also assess the safety, tolerability, and palatability of etrasimod mini tablets (total dose of 2 mg) in healthy adult participants. The etrasimod mini tablets are intended for dosing in pediatric population 2 years old to <12 years old.

This SAP provides the detailed methodology for summary and statistical analyses of the data collected in Study C5041034.

2.1. Modifications to the Analysis Plan Described in the Protocol

None.

2.2. Study Objectives and Endpoints

Objectives	Endpoints
Primary:	Primary:
• To estimate the rBA of etrasimod 2 mg mini tablets mixed with water compared with etrasimod 2 mg clinical IR tablets under fasted conditions	• Plasma AUC _{lasb} AUC _{inf} and C _{max} of etrasimod
• To estimate the rBA of the etrasimod 2 mg mini tablets mixed with apple sauce compared with the etrasimod 2 mg clinical IR tablets under fasted conditions	

Objectives	Endpoints
• To estimate the rBA of the etrasimod 2 mg mini tablets mixed with chocolate pudding compared with the etrasimod 2 mg clinical IR tablets under fasted conditions	
• To estimate the rBA of the etrasimod 2 mg mini tablets mixed with yogurt compared with the etrasimod 2 mg clinical IR tablets under fasted conditions	
Secondary:	Secondary:
• To evaluate the safety and tolerability of etrasimod in healthy participants	• Assessment of first dose HR reduction, TEAEs, clinical laboratory abnormalities, vital signs, PEs, and 12-lead ECGs
• To assess the palatability of etrasimod mini tablets mixed with water/apple sauce/chocolate pudding/yogurt	• Assessment of palatability via questionnaire: mouth feel, bitterness, tongue/mouth burns, throat burn, and overall liking
Tertiary/Exploratory:	Tertiary/Exploratory:
• To characterize the PK parameters of etrasimod 2 mg mini tablets mixed with water or soft foods (apple sauce, chocolate pudding, or yogurt) compared with etrasimod 2 mg clinical IR tablet	• Plasma etrasimod: t _{1/2} , CL/F, V _z /F and T _{max} of etrasimod
• To validate the PK measurement of etrasimod in capillary blood sample collected using a micro sampling device against the PK measurement of etrasimod in venous blood samples.	• Plasma concentration of etrasimod obtained via micro sampling compared to venous sampling

2.3. Study Design

This is a Phase 1, open-label, single-dose, randomized 4-crossover periods and 1-fixed period design in a single cohort of approximately 16 healthy male or female participants .

The study will consist of 5 treatments as shown below:

- 1. Treatment A: Single oral dose of etrasimod 2 mg clinical IR tablet under fasted conditions (Reference)
- 2. Treatment B: Single oral dose of etrasimod 2 mg mini tablets mixed with applesauce under fasted conditions (Test 1)
- 3. Treatment C: Single oral dose of etrasimod 2 mg mini tablets mixed with chocolate pudding under fasted conditions (Test 2)
- 4. Treatment D: Single oral dose of etrasimod 2 mg mini tablets mixed with water under fasted conditions (Test 3)
- 5. Treatment E: Single oral dose of etrasimod 2 mg mini tablets mixed with yogurt under fasted conditions (Test 4)

Sixteen participants will be enrolled in Period 1 for a total of 12 evaluable participants to complete study. Participants will be randomly assigned to 1 of the 4 sequences shown in Table 2 in which participants are randomized in crossover design to receive Treatments A to D in Periods 1 to 4 with Treatment E being fixed in Period 5. Participants will be discharged on Day 9 of Period 5, following completion of all assessments. Each treatment is 9 days that includes dosing, PK sampling and an extra day to minimize any residual etrasimod concentrations prior to start of the next treatment. The total planned duration of participation from the screening visit to the last follow-up phone call, is approximately 14 weeks.

Table 2. Treatment Sequence

Treatment sequence (n=4 per sequence)	Period 1	Period 2	Period 3	Period 4	Period 5 (fixed)
1	A	В	С	D	Ε
2	В	D	A	С	Ε
3	С	A	D	В	Ε
4	D	С	В	A	Ε

Since etrasimod has a half-life approximately 30 hours, there will be a 9-day washout between each dose.

3. ENDPOINTS AND BASELINE VARIABLES: DEFINITIONS AND CONVENTIONS

3.1. Primary Endpoints

The primary endpoints are the plasma AUC_{last}, AUC_{inf} and C_{max} of etrasimod. The test/reference ratios for AUC_{last}, AUC_{inf} and C_{max} will be derived with Treatment B (etrasimod 2 mg mini tablets mixed with applesauce under fasted conditions), Treatment C (etrasimod 2 mg mini tablets mixed with chocolate pudding under fasted conditions), and Treatment D (etrasimod 2 mg mini tablets mixed with water under fasted conditions) as the test treatments and Treatment A (etrasimod 2 mg clinical IR tablets under fasted conditions) as the reference treatment. In addition, the test/reference ratios for AUC_{last}, AUC_{inf} and C_{max} will be derived with Treatment E (etrasimod 2 mg mini tablets mixed 2 mg mini tablets mixed 2 mg mini tablets under fasted conditions) as the reference treatment A (etrasimod 2 mg mini tablets mixed 2 mg mini tablets mixed 2 mg mini tablets mixed 2 mg mini tablets under fasted conditions) as the reference treatment E (etrasimod 2 mg mini tablets mixed 2 mg mini tablets mixed 2 mg mini tablets mixed 2 mg clinical IR tablets under fasted conditions) as the reference 5 mixed 2 mg mini tablets mixed 3 mg mini tablets

Plasma PK parameters of etrasimod will be derived (as data permit) from the concentration-time data using standard noncompartmental methods as outlined in the Table 3 below. Actual PK sampling times will be used in the derivation of PK parameters. In the case that actual PK sampling times are not available, nominal PK sampling time will be used in the derivation of PK parameters.

DMB02-GSOP-RF02 7.0 Statistical Analysis Plan Template 31-Jan-2022 PFIZER CONFIDENTIAL TMF Doc ID: 98.03 Page 7 of 20

Parameter	Definition	Method of Determination	
AUCinf	Area under the concentration-time curve from time zero extrapolated to infinity	$AUC_{last} + (C_{last}*/k_{el}),$ where $C_{last}*$ is the predicted plasma concentration at the last quantifiable time point from the log-linear regression analysis	
AUClast	Area under the plasma concentration-time profile from time zero to the time of the last quantifiable concentration (C_{last})	Linear/Log trapezoidal method.	
C_{max}	Maximum observed concentration	Observed directly from data	
T_{max}	Time for C _{max}	Observed directly from data as time of first occurrence	
t ½	Terminal half-life	$Log_e(2)/k_{el}$, where k_{el} is the terminal phase rate constant calculated by a linear regression of the loglinear concentration-time curve. Only those data points judged to describe the terminal loglinear decline will be used in the regression.	
CL/F	Apparent clearance	Dose/AUC _{inf}	
V_z/F	Apparent volume of distribution	$Dose/(AUC_{inf} \bullet k_{el})$	

Table 3.Definitions of PK Parameters

3.2. Secondary Endpoints

3.2.1. Safety data

The secondary endpoints include the safety and tolerability data, discussed in Section 3.5.

3.2.2. Palatability of etrasimod mini tablets

The data collected for palatability assessment using the sponsor-provided palatability questionnaire will be numerically derived by measuring length (using a scale with gradations of at least 0.1 cm) of the "x" marked by the participant relative to the "good trait". For palatability assessment, the data used in the analysis will be transcribed and rescaled to a score from 0 to 100 from the raw measurements on the questionnaire.

3.3. Baseline Variables

Baseline characteristics will be collected according to the schedule of activities (SoA) as specified in the protocol.

3.4. Other Endpoints

3.4.1. Other PK parameters of etrasimod

Exploratory endpoints include other plasma PK parameters of etrasimod such as $T_{max},\,t_{1/2},\,CL/F$ and $V_z/F.$

DMB02-GSOP-RF02 7.0 Statistical Analysis Plan Template 31-Jan-2022 PFIZER CONFIDENTIAL TMF Doc ID: 98.03 Page 8 of 20

3.4.2. Etrasimod microsampling concentration

Etrasimod micro sampling concentration using Tasso device will be collected according to the SoA as specified in the protocol.

3.5. Safety Endpoints

The following data are considered in standard safety summaries (see protocol for collection days, baseline assessment, and list of parameters):

- first dose HR reduction
- adverse events (AE)
- laboratory data
- vital signs data
- electrocardiogram (ECG) results

3.5.1. First Dose HR reduction

For all periods, HR will be measured every hour up to 6 hours, at 8 and 24 hours postetrasimod dose at Day 1. The baseline HR value is the average of the HR values from the triplicate ECG measurements collected predose on Day 1 of each period. Changes from baseline will be defined as the change between the postdose measurements and baseline value. In addition, the nadir HR value on Day 1 will be derived.

3.5.2. Adverse Events

Any adverse events occurring following start of treatment will be considered as treatment emergent adverse event (TEAE). Events that occur during follow-up within the lag time of up to 35 days after the last dose of study intervention will be counted as treatment emergent and attributed to the last treatment taken. The time period for collecting AEs ("active collection period") for each participant begins from the time the participant provides informed consent.

3.5.3. Laboratory Data

Safety laboratory tests will be performed as described in the protocol. To determine if there are any clinically significant laboratory abnormalities, the haematological, clinical chemistry (serum) and urinalysis safety tests will be assessed against the criteria specified in the sponsor reporting standards. The assessment will not take into account whether each participant's baseline test result is within or outside the laboratory reference range for the particular laboratory parameter.

For all periods, the baseline measurement is the predose measurement on Period 1 Day -1. Changes from baseline will be defined as the change between the postdose and baseline measurements.

DMB02-GSOP-RF02 7.0 Statistical Analysis Plan Template 31-Jan-2022 PFIZER CONFIDENTIAL TMF Doc ID: 98.03 Page 9 of 20

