Days Relative to Day 1 in Each Period	Day -28 to Day -2	Day -1	Day 1	Days 2-8	Day 9			
 
Participants will be screened within 28 days of the first dose of study intervention.
 
Follow-up contact will occur by telephone and must occur at least 28 to 35 days after the last administration of etrasimod (Day 1 of Period 5 if dosing completed).
 

Period 1 Study Days	-28 to -2	-1	1	2-8	9			
Period 2 Study Days			10	11-17	18			
Period 3 Study Days			19	20-26	27			
Period 4 Study Days			28	29-35	36			
Period 5 Study Days			37	38-44	45	65-72		
 
Participants will be discharged on Day 9 of Period 5.
 

Safety laboratory	X	X		X*	X		X	
 
Safety laboratory screening testing must be collected, reported, and reviewed within 28 days prior to first administration of study intervention.
 
Safety laboratory assessments including urinalysis, hematology, and chemistry will be performed. Participants should fast for at least 4 hours prior to any safety blood collection. Additional laboratory assessments may be performed if deemed necessary by the investigator.
 
*Safety laboratory assessment will be only performed on Day 2 of each period.
 
If labs are not within normal range on Day 9 of Period 5, unscheduled follow-up visits will occur per protocol.
 
Refer to Table 5 for full list of assessments
 

Urine drug testing	Х	Х						
Pregnancy test (WOCBP only)	Х	Х						
 
Given that the participant will be confined in CRU for the entire study, if tested negative on Day -1, no further test is needed unless otherwise specified.
 
See Table 5 for more details.
 

Visit Identifier Abbreviations used in this table may be	Screen	Period 1 Check	]	Periods 1-	5	F/U Telephone	ET	Notes
found in Appendix 10 Days Relative to Day 1 in Each Period	Day -28 to Day -2	In Day -1	Day 1	Days 2-8	Day 9	Contact		
 
Participants will be screened within 28 days of the first dose of study intervention.
 
Follow-up contact will occur by telephone and must occur at least 28 to 35 days after the last administration of etrasimod (Day 1 of Period 5 if dosing completed).
 

Period 1 Study Days	-28 to -2	-1	1	2-8	9			
Period 2 Study Days			10	11-17	18			
Period 3 Study Days			19	20-26	27			
Period 4 Study Days			28	29-35	36			
Period 5 Study Days			37	38-44	45	65-72		• Participants will be discharged on Day 9 of Period 5.

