	dosing without major clinically relevant cardiac safety events.	
Reproductive and developmental toxicity.	The effects of etrasimod on human fertility and embryonic development are unknown.	WOCBP who are pregnant, lactating, or breastfeeding will be excluded from this study.
	Nonclinical reproductive and developmental toxicity studies of etrasimod combined with data and knowledge on the role of S1P 1 in vascular embryogenesis demonstrate embryo fetal toxicity of etrasimod if used during pregnancy. Etrasimod is potentially teratogenic in humans with a low genotoxic potential. There is no margin of safety for these findings compared to therapeutic exposure range. Etrasimod should not be given to women who are pregnant, lactating or breastfeeding	

WOCBP will be eligible only if she and her partner(s) agree(s) with the contraceptive method as described in Section 10.4.4 throughout the study period and for at least 28 days after the last dose of etrasimod.

Males with female partners of childbearing potential must agree to use contraception throughout the study period and for at least 28 days after the last 28 days after the last dose of etrasimod.

	Study Procedures Blood Collection for PK	
Extravasation, bruising, local discomfort	Collection of 14 PK plasma samples per period per sequence	Use of highly qualified nurses, with venipuncture experience.
	Collection of 8 PK micro samples collected for Treatment A.	Use of alternating arms for adjacent time points can provide more resting and healing time for each arm between samplings.

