3.5.4. Vital Signs

Supine blood pressure (BP), pulse rate (PR) and temperature will be measured at times specified in the SoA given in the protocol.

For all periods, the baseline measurement is the predose measurement on Day 1 in each period. Changes from baseline will be defined as the change between the postdose and baseline measurements.

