3.5.5. Electrocardiograms

QT interval, QTcF, PR interval, QRS and heart rate (HR) will be recorded at each 12-lead ECG assessment time indicated in the SoA given in the protocol. QTcF will be derived using Fridericia's heart rate correction formula:

 $QTcF = QT / (RR)^{(1/3)}$ where RR = 60/HR (if not provided)

For all periods, the baseline value is the average of triplicate ECG measurements collected predose on Day 1 of each period. Changes from baseline will be defined as the change between the postdose measurements and baseline value.

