6.6.3. Laboratory Data

Laboratory data will be listed and summarized by treatment in accordance with the CaPS.

DMB02-GSOP-RF02 7.0 Statistical Analysis Plan Template 31-Jan-2022 PFIZER CONFIDENTIAL TMF Doc ID: 98.03 Page 15 of 20

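### Laboratory change from baseline uses one Period 1 Day -1 value throughout, so Treatment E, always given fifth, carries the drift of the whole study

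*SAP*

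**What the plan says.** - **Laboratory baseline (SAP 3.5.3):** "For all periods, the baseline measurement is the predose measurement on Period 1 Day -1". The section continues: "Changes from baseline will be defined as the change between the postdose and baseline measurements".
- **Laboratory reporting (SAP 6.6.3):** "Laboratory data will be listed and summarized by treatment in accordance with the CaPS".
- **Other safety measures:** for vital signs (SAP 3.5.4), "For all periods, the baseline measurement is the predose measurement on Day 1 in each period". For ECGs (SAP 3.5.5), "For all periods, the baseline value is the average of triplicate ECG measurements collected predose on Day 1 of each period". First-dose heart rate (SAP 3.5.1) also uses the predose triplicate of the same period.
- **Order of treatments (SAP 2.3):** participants receive "Treatments A to D in Periods 1 to 4 with Treatment E being fixed in Period 5".
- **Laboratory schedule (Protocol 1.3):** the safety laboratory row is marked at screening, Day -1, the Days 2-8 column, Day 9 and early termination. A note narrows the Days 2-8 mark: "Safety laboratory assessment will be only performed on Day 2 of each period". The Day 9 mark sits under Periods 1-5. The ECG and vital sign rows limit Day 9 to Period 5; the laboratory row does not. No period has a Day 1 predose laboratory draw.
- **Abnormality criteria (SAP 3.5.3):** these follow sponsor standards and disregard whether the baseline result was in range.

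Neither document gives a reason for the different laboratory rule or adjusts for it.

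**The concern.** A change from baseline summarised by treatment invites the reader to attribute it to that treatment. For A to D, a fixed Day -1 baseline adds noise but little bias between them, because each occupies Periods 1 to 4 once. E has no such balance. Its laboratory samples fall on study Days 38 and 45, after doses on Days 1, 10, 19 and 28, so its 24-hour response is measured against a value taken 38 days earlier.

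Anything that drifts over the stay enters E's change in full. The clearest candidates are haemoglobin, haematocrit and red cell count, which fall with repeated sampling. A table by treatment could then show the yogurt vehicle with the largest fall for reasons that have nothing to do with yogurt.

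**Working it through.** **1. Earlier periods inside the change window.** The four sequences are ABCDE, BDACE, CADBE and DCBAE. The number of earlier periods is 0, 1, 2 and 3, once each, for A, B, C and D: mean (0+1+2+3)/4 = 1.5. For E it is 4 in every sequence. Excess for E: 4 - 1.5 = 2.5 periods, or 2.5 x 9 = 22.5 days.

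**2. The plan's own blood volume.** Protocol 8.1 gives about 382 mL in total. The documented parts are:
- PK: "Collection of 14 PK plasma samples per period per sequence" at about 4 mL each (Protocol 8.5), so 14 x 4 = 56 mL per period and 5 x 56 = 280 mL in all.
- Micro samples: 8 x 0.5 = 4 mL, Treatment A only.
- Safety biomarker: 10 mL, Period 1 Day 1 only.

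Sum: 280 + 4 + 10 = 294 mL. The volume of a safety laboratory draw is not given, so 382 mL cannot be fully reproduced; 382 - 294 = 88 mL is unassigned.

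**3. Excess sampling before E.**
- Documented PK volumes only: 2.5 x 56 = 140 mL.
- With the 88 mL spread over 12 draws (screening, Day -1, Days 2 and 9 of five periods): 88/12 = 7.3 mL per draw; 56 + 2 x 7.3 = 70.7 mL per period; 2.5 x 70.7 = 177 mL.
- If Day 9 draws occur only in Period 5, there are 8 draws: 88/8 = 11 mL; 56 + 11 = 67 mL per period; 2.5 x 67 = 168 mL.

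The last two assume that the 382 mL includes the Day 2 draws and that screening serology and TB tests take none of the 88 mL. The biomarker sample precedes every treatment's Day 2 sample, and micro samples shift the comparison by at most 4 mL; both are left out.

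**4. Haemoglobin ceiling.** Assume blood volume V of 4 to 6 L, haemoglobin 14 g/dL, plasma volume restored and no red-cell regeneration. Difference = 14 x excess / V.

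| Excess | V = 6 L | V = 4 L |
|---|---|---|
| 140 mL | 0.33 g/dL | 0.49 g/dL |
| 177 mL | 0.41 g/dL | 0.62 g/dL |

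**5. Drug carryover.** Nine days is 216 h. With a half-life of about 30 h that is 7.2 half-lives, and 0.5^7.2 = 0.7% remains at the next dose. Protocol 2.3.1 reports lymphocytes back in the normal range by Day 7 after a single dose.

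**6. Effect of a period baseline.** This takes 7.3 mL per laboratory draw and counts the baseline draw itself.
- Day -1 up to the Period 5 dose: 4 x 56 + 4 + 10 + 9 x 7.3 = 304 mL.
- Window to E's Day 2 sample (seven PK samples precede it): 304 + 28 = 332 mL.
- Window to E's Day 9 sample: 304 + 56 + 7.3 = 367 mL.
- Same windows from Day 9 of Period 4: 7.3 + 28 = 35 mL and 7.3 + 56 + 7.3 = 71 mL.

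**The case against.** The case for leaving the rule alone has several parts, and much of it stands.

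- **Endpoint.** The secondary endpoint names laboratory abnormalities, and the criteria for these disregard baseline status. A reader might infer that E's abnormality counts would change with the baseline; SAP 3.5.3 does not support that.
- **No table is promised.** SAP 6.6.1 and 6.6.5 commit to changes from baseline by treatment for heart rate and ECG. SAP 6.6.3 only defers to sponsor standards that are not in the documents. A laboratory change table is therefore inferred from the fact that SAP 3.5.3 defines the change. That is reasonable but not certain.
- **The schedule explains the difference.** Vital signs and ECGs have a predose Day 1 measurement in every period; laboratory tests do not. Day -1 is also the last value before any drug. This is a good reason to keep that column, but not to make it the only one.
- **Carryover.** A reader might infer that E is charged with the drug effect of four earlier doses. The 0.7% residual and the reported lymphocyte recovery argue against a large effect. Being back in the normal range is not the same as being back at one's own baseline, but the documents give no figure for any remainder.
- **Day 9 samples.** That they exist in every period rests on one mark in the schedule. The same row mentions follow-up only for Day 9 of Period 5, and Protocol 2.3.1 lists safety laboratory tests only at screening, at baseline and when needed. The contrast with the ECG and vital sign rows favours the every-period reading, but it should be confirmed.

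**Conclusion.** The point holds as a limited one about descriptive change from baseline. E's laboratory change always spans four earlier periods against a balanced mean of 1.5 for A to D, and the documents do not correct for this. The mechanism is mainly cumulative sampling, about 140 to 177 mL more than the A-D mean, together with about five weeks of confinement.

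The 0.3 to 0.6 g/dL haemoglobin figure is a ceiling, not a forecast. It rests on assumed blood volume and haemoglobin, and its upper end also on assumed laboratory draw volumes. It allows no regeneration over five weeks, so the true figure is probably smaller. The documents give nothing from which to set a realistic lower value. The direction is against E.

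A reader might go further and conclude that the safety comparison of the yogurt vehicle is invalid. The documents do not support that: no hypothesis is tested, individual laboratory values are listed, the abnormality criteria disregard baseline status, and the PK results do not use this baseline.

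**What to change.** In SAP 3.5.3, define a second change: from the last laboratory value before that period's dose, which is Day -1 for Period 1 and Day 9 of the preceding period for Periods 2 to 5. Keep change from Period 1 Day -1 beside it as the drug-free, cumulative column. In SAP 6.6.3, state that both are summarised by treatment.

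The cost is a sentence or two in the SAP and one extra summary column. No new samples are needed if the schedule's laboratory row means what it appears to say; confirm first that Day 9 laboratory samples are taken in every period, since otherwise Periods 2 to 5 have no such value.

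Two limits remain and should be stated with the table. The Day 9 value follows a prior dose by 8 days (192/30 = 6.4 half-lives; 0.5^6.4 = 1.2% remaining), so it is not drug-free. And a period baseline removes drift up to Period 5 only: E stays confounded with Period 5, and its absolute values still carry the cumulative blood loss.
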